- Investigators may gently remove an obstacle that is blocking the ear canal if it prevents IP application or causes subjects to experience an uncomfortable sensation. If the obstacle is adherent to the tympanic membrane, it should not be removed; it is recommended to wait until the obstacle comes off.
- Subjects should refrain from activities that can increase the middle ear pressure including plane travel (at least 28 days after IP application), positive pressure ventilation (e.g., CPAP or BiPAP) devices, Valsalva maneuvers, excessive high-pressure nose blowing, or diving underwater.
- Subject must refrain from activities that can excessively increase body temperature (e.g. Sauna) for at least 3 days after IP application.
- Subject must refrain from activities that stimulate sweating excessively for at least 3 days after IP application.

Duration of Treatment:

SAD and single dose expansion: Topical application into the affected ear on Day 1.

MAD: Topical application into the affected ear on Days 1, 15, and 29.

Multiple Dose Expansion: Topical application into the affected ear on Day 1 and if the subject has not achieved complete closure of the TMP at Day 15 and Day 29, additional treatment will occur. If the subject achieves complete closure on either Day 15 or Day 29, no additional treatment is required at those visit(s).

Treatment Discontinuation Criteria:

SAD and single dose expansion

Not applicable because there is a single treatment of ASP0598 Otic Solution or placebo.

MAD and multiple dose expansion

Treatment Discontinuation

During the course of IP administration, if the subject experiences a drug-related adverse event (AE), the IP administration may be discontinued at the investigator's discretion.

In addition, IP administration will be discontinued if severe intensity occurs in any of the following situations:

- Subject develops cholesteatoma or suspicion of neoplasm in the treated ear as determined by the investigator.
- Subject develops suspected ototoxicity symptoms (e.g., sudden hearing loss at high frequencies (1, 2, 4 kHz), new high frequency tinnitus or new balance disorder) which are considered by the investigator to be related to the study drug.
- Subjects with persistent otitis media or otitis externa unresponsive to oral and topical antibiotics (as described in Previous and Concomitant Treatment [Medication and Nonmedication Therapy of the synopsis and protocol Section 6.5])

Dose Escalation:

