1.2 Study Schema

Figure 1 Study Design Schema

[figure not shown]

★ Dose Escalation Committee (DEC) Meeting

★ Interim Analysis (IA)

[figure not shown]
A: active; P: placebo; L: low-dose ASP0598; H: high-dose ASP0598

Figure 2 Study Flow Chart – SAD

[figure not shown]
CBC: complete blood count; PK: pharmacokinetic; SAD: Single Ascending Dose

Figure 3 Study Flow Chart – Single Dose Expansion

[figure not shown]
CBC: complete blood count

Figure 4 Study Flow Chart – MAD

CBC: complete blood count; MAD: Multiple Ascending Dose; PK: pharmacokinetic

[figure not shown]
Figure 5 Study Flow Chart – Multiple Dose Expansion

* Additional treatments on Day 15 and 29 will be conducted if the subject has not achieved complete closure of TMP.

CBC: complete blood count

[figure not shown]
Figure 6 Otology Examination and PK Blood Draw Flow Chart – Single Dose

Through Day 29 (SAD) or through Day 57 (Single Dose Expansion)

Day 57 (SAD), Day 85 (Single Dose Expansion) or EOS

[figure not shown]
Footnotes appeared on next page

EOS: end of study; PK: pharmacokinetic; PTA: Pure Tone Audiometry; SAD: single ascending dose; TM: tympanic membrane; VAS: Tinnitus Visual Analog Scale

- a. After ASP0598 Otic Solution or placebo administration, subjects will be required to remain on their side with the treated ear facing up for at least 15 minutes. Please see the Pharmacy Manual, Section 9.4: Dose Administration for detailed instructions.
- b. Day 1, imaging picture will be taken pre-dose, immediately after, 30 (± 5) minutes and 60 (± 5) minutes after ASP0598 Otic Solution or placebo administration into the affected ear.
- c. PK blood samples will be collected on Day 1 at pre-dose (-15) minutes and at the following post-dose time points: 30 (± 5) minutes and 60 (± 5) minutes. PK blood sampling will be performed only in SAD after ASP0598 Otic Solution or placebo administration into the affected ear.
- d. Skin local reaction at the ASP0598 Otic Solution/placebo application site will be evaluated by Modified Brighton Grading Scheme (Appendix [12.9](#)) at all visits.
- e. Ear cleaning will not be conducted between Days 2 – 29 (SAD) or Days 2 – 57 for (single dose expansion), unless it is absolutely necessary. Investigators will not clean the treated ear by suctioning unless subjects experience uncomfortable ear discharge).

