- d. ASP0598 Otic Solution or placebo will be applied onto the remaining tympanic membrane under a microscope with a 22-gauge blunt needle. After ASP0598 Otic Solution or placebo administration, subjects will be required to remain on their side with the treated ear facing up for at least 15 minutes. Please see the Pharmacy Manual, Section 9.4: Dose Administration for detailed instructions.
- e. Otology examinations will be performed for both ears at the screening visit.
- f. Microscopic Ear examination will be performed prior to and 60 (± 5) minutes after ASP0598 Otic Solution/placebo administration. Skin local reaction at the application site will be evaluated by Modified Brighton Grading Scheme (Appendix 12.9) at 60 (± 5) minutes after ASP0598 Otic Solution/placebo administration.
- g. Ear cleaning will not be conducted between Days 2 – 85, unless it is absolutely necessary. Investigators will not clean the treated ear by suctioning unless subjects experience uncomfortable ear discharge).
- h. At Days 1, 15, and 29, imaging pictures will be taken at the following time points: pre-dose, immediately after, 30 (± 5) minutes, and 60 (± 5) minutes after the ASP0598 Otic Solution or placebo administration.
- i. At Day 85 (SAD) or Day 113 (single dose expansion) and/or EOS, the whole TM should be visible before taking imaging picture. If the whole TM is not visible, the investigator should clean the ear canal.
- j. Bone conduction testing at Day 15, 29, 43, 57, and 85 will be tested only at 1, 2 and 4 kHz (ototoxicity assessment).
- k. Urine or serum pregnancy test will be performed in women of childbearing potential.
- l. ASP0598 Otic Solution or placebo administration on Day 15 and Day 29 will be conducted in the case that the TMP closure is not confirmed.

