3.2.2 Treatment regimen under evaluation

Randomized treatment administered as directed per Schedule of Assessments.

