Subjects who terminate early from the study will complete EOS assessments at the time of discontinuation.

Multiple Dose Expansion

After randomization on Day 1, subjects will receive ASP0598 Otic Solution or placebo administration into the affected ear. Subjects may receive additional treatment in the same

ear on Days 15 and 29. Subjects will return to the investigative site for assessments on Days 15, 29, 43, 57, 85 and 113 (EOS).

In cases where complete closure is confirmed on Day 15 or Day 29, the subject will not receive the next scheduled dose(s), but will complete all visit assessments as defined in the Schedule of Assessments through Day 113.

Subjects who terminate early from the study will complete EOS assessments at the time of discontinuation.

Subjects who discontinue treatment will be encouraged to complete all protocol defined study visits through the Day 113.

In single dose expansion and/or multiple dose expansion, subjects may be replaced at the discretion of the sponsor. If replaced, the replacement subject will be given the same treatment group the original subject's randomized treatment group.

4.1.1 Decision Process for Dose Escalation, Dose Escalation Stopping Rules and Definition of the Maximum Tolerated Dose

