6.6 Dose Modification

SAD and single dose expansion

Not Applicable.

MAD

On Day 15 or Day 29, treatment can be skipped at the Investigator's discretion based on safety reasons that interrupt IP administration (e.g., ear canal skin irritation, mild otorrhea). Subjects should be encouraged to return to the office for evaluation and additional IP administration within the Day 15 or Day 29 visit windows. In the case that the investigator is unable to conduct IP administration for anything other than safety reasons, consultation with the sponsor may be required.

Multiple dose expansion

The statement above for MAD is also applicable to the multiple dose expansion. Additionally, the treatment on Day 15 or Day 29, treatment will be skipped in cases where complete closure is confirmed. If the perforation is detected on Day 29 after treatment was skipped on Day 15, IP administration can be conducted.

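### In multiple dose expansion, the protocol gives inconsistent instructions on the Day 29 dose for an ear confirmed closed on Day 15 and found open on Day 29

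*Protocol*

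**What the plan says.** Three kinds of instruction govern the Day 15 and Day 29 doses in multiple dose expansion.

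- **Withhold after closure.** Protocol section 4.1 (Multiple Dose Expansion) and the synopsis paragraph of the same name: "In cases where complete closure is confirmed on Day 15 or Day 29, the subject will not receive the next scheduled dose(s". The rest of that sentence keeps the subject in the visit schedule through Day 113. It does not mention re-opening.
- **Permit after re-opening.** Section 6.6 and the Dose Modifications text of the synopsis: "If the perforation is detected on Day 29 after treatment was skipped on Day 15, IP administration can be conducted". The same paragraph carries over the investigator's discretion to skip a dose for safety reasons: "The statement above for MAD is also applicable to the multiple dose expansion".
- **Give if not closed.** Table 5 footnote l in section 1.3: "administration on Day 15 and Day 29 will be conducted in the case that the TMP closure is not confirmed". Figure 7 footnote h and Table 16 footnote l (section 12.11) state the same rule. The Figure 5 footnote reads: "Additional treatments on Day 15 and 29 will be conducted if the subject has not achieved complete closure of TMP". The Duration of Treatment text in the synopsis says "if the subject has not achieved complete closure of the TMP at Day 15 and Day 29, additional treatment will occur" and, for a closed ear, "no additional treatment is required at those visit(s".

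The estimand defines the regimen in protocol section 3.2.2 as "Randomized treatment administered as directed per Schedule of Assessments". SAP section 5.3.1 repeats this definition. Neither document says which text prevails where they differ.

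**The concern.** The protocol foresees the re-opened ear, since section 6.6 was written for it, yet a site's action depends on the page it reads. The synopsis alone contains all three instructions.

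Three things are at stake:

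- **Exposure.** The number of doses is a reported quantity (protocol section 9.3.5, SAP section 6.3), and SAP section 6.5.4 summarises local skin reactions by second and third dose.
- **The estimand.** Its regimen points to the Schedule of Assessments, so a site that follows section 4.1 on its natural reading departs from the regimen under evaluation.
- **Consistency between sites.** Re-opened ears could be treated differently at different sites, in arms of only 13 subjects.

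**Working it through.** The plan states no figure on this point, so there is none to reproduce. The check applies each text to one case: complete closure confirmed on Day 15, Day 15 dose skipped, perforation present on Day 29, no safety reason to skip.

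| Text | Day 29 dose for this ear | Total doses |
|---|---|---|
| Section 4.1; synopsis, Multiple Dose Expansion | Withheld, on the natural reading | 1 |
| Section 6.6; synopsis, Dose Modifications | Allowed | 1 or 2 |
| Table 5 footnote l; Table 16 footnote l; Figure 7 footnote h; Figure 5 footnote; synopsis, Duration of Treatment | Given | 2 |

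**Step 1: what the section 4.1 sentence means.** For closure on Day 15, the next scheduled dose is most naturally the one on Day 29. The plural and the missing exception for re-opening support that. For closure first seen on Day 29 the phrase has no referent, because no later dose is scheduled. There it can only mean the dose due at that same visit. Applying that meaning to Day 15 as well gives a visit-by-visit rule under which the Day 29 dose is not barred. This is possible, but it strains the word *next*.

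**Step 2: whether the visit-by-visit reading removes the conflict.** It reconciles section 4.1 with the footnotes. It does not reconcile section 6.6, where the dose *can* be given, with the footnotes and the Duration of Treatment text, where it *will* be given. One leaves a choice and the other does not.

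**Step 3: the difference in exposure.** The expansion doses are still to be selected, so the planned MAD concentrations at 0.15 mL serve as an illustration:

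- 5 µg/mL: 1 × 5 × 0.15 = 0.75 µg against 2 × 5 × 0.15 = 1.50 µg.
- 15 µg/mL: 1 × 15 × 0.15 = 2.25 µg against 2 × 15 × 0.15 = 4.50 µg.

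Total exposure differs by a factor of two.

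**Step 4: the most one subject can contribute to the closure rate.** With the planned 13 subjects in an arm, 1/13 = 0.077, or 7.7 percentage points. That bound is reached only if giving or withholding the Day 29 dose changes that ear's Week 16 closure status.

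**The case against.** The best defence has three parts.

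- **Section 4.1 may not bar the dose.** The visit-by-visit reading agrees with the Duration of Treatment text, which ties the waiver to the visit at which closure is seen. This softens the bar but leaves *can* against *will*.
- **Section 6.6 addresses this exact case.** A site facing a re-opened ear has specific text in the dose-modification section, while section 4.1 is a general design description. That helps in practice. Without a precedence clause it does not override the Schedule of Assessments, to which the estimand points.
- **The consequences are limited.** Closure is a secondary endpoint, the primary endpoints are safety endpoints without hypothesis testing, and this part opens only if the DMC so decides. All of this stands, and it limits the weight of the point.

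A reader might also infer more than the documents support:

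- *That dosing is barred through Day 113.* That phrase governs visit assessments, not doses.
- *That the Day 29 dose is unconditionally required.* Section 6.6 keeps the safety skip.
- *That affected cases would be logged as a wrong-dose deviation (PD3).* Nothing says that following one of the protocol's own texts would be classed that way.
- *That a large shift in the closure rate can be forecast.* Assuming 20–60% of 13 active ears closed on Day 15 and 10–30% of those re-opened gives 13 × 0.2 × 0.1 = 0.3 to 13 × 0.6 × 0.3 = 2.3 subjects. Two subjects would be 2/13 = 15.4 points. The documents supply neither rate, and the conversion assumes that the Day 29 dose alone decides Week 16 closure.

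**Conclusion.** The inconsistency is real. Texts of apparently equal standing lead to one dose, one or two, or two doses for the same ear. The section 4.1 bar depends on the natural, though not the only, reading of its phrase. The conflict between permission and instruction does not depend on that reading. What is affected is the dose count, exposure and adherence to the estimand regimen.

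The effect on the closure result cannot be estimated. The number of affected subjects may be zero, and 7.7 points is a ceiling per subject at 13 per arm, not a predicted bias. The point still warrants correction before multiple dose expansion enrols, because it concerns when study drug is given and the repair is small.

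**What to change.** Reconcile these nine places into one instruction that treats Day 15 and Day 29 visit by visit:

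- synopsis: Multiple Dose Expansion, Dose Modifications, and Duration of Treatment;
- section 1.2: the Figure 5 footnote and Figure 7 footnote h;
- section 1.3: Table 5 footnote l;
- section 4.1, Multiple Dose Expansion;
- section 6.6;
- section 12.11: Table 16 footnote l.

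The instruction should cover an ear that is closed at the visit, one that is open, and one that is open again after a skipped dose. It should use a single verb for the last case, state how the safety skip applies, and replace the section 4.1 phrase that has no referent on Day 29. Which rule applies is for the sponsor to decide. Protocol section 3.2.2 and SAP section 5.3.1 should then refer to that same rule.

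The cost is protocol and SAP wording only. No visits, subjects or analyses are added.

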6.3.6 Assignment and Allocation

SAD

In each cohort, a total of 5 subjects will be randomized in a 4:1 ratio of ASP0598 Otic Solution (4 subjects) and placebo (1 subject).

MAD

In each cohort, a total of 8 subjects will be randomized in a 6:2 ratio of ASP0598 Otic Solution (6 subjects) and placebo (2 subjects).

Dose Expansion

- Based on the interim analysis results, if 3 treatment groups are selected, approximately 39 subjects will be randomized in a 1:1:1 ratio of high dose ASP0598 Otic Solution, low dose ASP0598 Otic Solution, or placebo (13 subjects in each treatment group).
- If 2 treatment groups are selected, approximately 26 subjects will be randomized in a 1:1 ratio of high dose ASP0598 Otic Solution or placebo (13 subjects in each treatment group).

Subjects will be stratified at the time of randomization by % size of the TMP ($\leq 15\%$, $> 15\%$) at the Screening Visit. Subjects will be balanced equally between the treatment groups.

TMP size group will be determined by the Screening images sent from the investigative site to the central imaging vendor.

For SAD, MAD, and dose expansion, randomization will be performed via IRT using central allocation. If a subject is assigned a randomization number, but does not receive study drug, the randomization number will not be used again. The randomization schedule that determines subject treatment will be computer-generated by IRT before the beginning of the study. The unblinded study site personnel will dispense the treatment according to the IRT system's assignment. Specific procedures for randomization through the IRT are contained in the study-specific IRT manual.

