9.1 Sample Size

SAD

Formal sample size calculations were not performed. SAD is not intended to show statistical difference between ASP0598 Otic Solution and placebo subjects.

A sample size of 5 per cohort ($n = 4$ ASP0598 Otic Solution, $n = 1$ placebo) is based on precedent set by other clinical studies of similar nature. The number of subjects and study procedures planned for this clinical study are considered reasonable to achieve the clinical study objectives.

MAD

Formal sample size calculations were not performed. MAD is not intended to show statistical difference between ASP0598 Otic Solution and placebo subjects.

A sample size of 8 per cohort ($n = 6$ ASP0598 Otic Solution, $n = 2$ placebo) is based on precedent set by other clinical studies of similar nature. The number of subjects and study procedures planned for this clinical study are considered reasonable to achieve the clinical study objectives.

Dose expansion

Assuming the complete closure rate in placebo and ASP0598 higher concentration group are 10% and 80% respectively, 11 subjects per treatment group will provide more than 90% power to detect a statistically significant difference at a 2-sided significance level of 0.05. Considering the drop-out rate of 10%, 13 subjects per treatment group will be enrolled (nQuery Advisor 7.0).

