2.3 Randomization

Dose escalation

Dose escalation will consist of up to 4 cohorts for single ascending dose (SAD) and up to 2 cohorts for multiple ascending dose (MAD). In each cohort of the SAD, a total of 5 subjects will be randomized in a 4:1 ratio of ASP0598 Otic Solution and placebo. In each cohort of the MAD, a total of 8 subjects will be randomized in a 3:1 ratio of ASP0598 Otic Solution and placebo.

For each cohort in SAD and MAD, a simple block randomization schedule will be generated.

Dose expansion

The decision to open the single and multiple dose expansion phases will be based on the safety and efficacy results of the interim analyses after completion of SAD and after completion of MAD, respectively.

Up to 39 subjects will be randomized to each of the single dose and/or multiple dose expansion phases of the study. Based on the interim analysis results,

- If 3 treatment groups are selected, approximately 39 subjects will be randomized in a 1:1:1 ratio of high dose ASP0598 otic solution, low dose ASP0598 otic solution and placebo (13 subjects in each treatment group).
- If 2 treatment groups are selected, approximately 26 subjects will be randomized in a 1:1 ratio of high dose ASP0598 otic solution (13 subjects) or placebo (13 subjects).

Stratification at the time of randomization will be based on the % size of the TMP ($\leq 15\%$, $> 15\%$) and subjects will be balanced equally between the treatment groups.

For all phases subjects may be replaced at the discretion of the sponsor. If replaced, the replacement subject will be given the same treatment group as the original subject's randomized treatment group. Randomization will be performed via interactive response technology (IRT) using central allocation. If a subject is assigned a randomization number, but does not receive study drug, the randomization number will not be used again. Specific procedures for randomization through the IRT are contained in the study-specific IRT manual.

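### In dose expansion a replacement inherits the departed subject's treatment and so bypasses the stratified randomisation; size-stratum balance can be disturbed, although the expected effect is small

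*Protocol*

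**What the plan says.** **Replacement.** Protocol 4.1, on dose expansion, states: "In single dose expansion and/or multiple dose expansion, subjects may be replaced at the discretion of the sponsor". It continues: "If replaced, the replacement subject will be given the same treatment group", meaning the group to which the departed subject was randomised. The synopsis repeats the rule. SAP 2.3 applies it throughout: "For all phases subjects may be replaced at the discretion of the sponsor". Neither document states a trigger, a time limit or a condition on the replacement's perforation size.

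**Randomisation.** Protocol 6.3.6 says of expansion: "Subjects will be stratified at the time of randomization by % size of the TMP", with categories of at most 15% and above 15% at Screening. It adds "Subjects will be balanced equally between the treatment groups" and "For SAD, MAD, and dose expansion, randomization will be performed via IRT using central allocation". If a randomised subject is never dosed, "the randomization number will not be used again". Further procedure is left to the IRT manual.

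**Sample size and analysis.** Protocol 9.1 raises 11 per group to 13: "Considering the drop-out rate of 10%, 13 subjects per treatment group will be enrolled". The FAS (protocol 9.2.1, SAP 4.1) takes every randomised subject with a dose, a baseline value and at least one post-baseline closure assessment. Neither definition mentions replaced subjects. Closure is tested by Mantel-Haenszel within baseline size group. If the Mantel-Fleiss criterion fails, the test is an unstratified Fisher test (protocol 9.4.2.1, SAP 6.4.2).

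**The concern.** The two rules sit side by side in SAP 2.3 and are not reconciled. Under 6.3.6 a new expansion subject gets a treatment drawn from the list for that subject's own stratum. Under the replacement rule the treatment is settled by who left and by the sponsor's decision to replace that person. Matching on stratum would cure the imbalance, but the treatment would still be inherited and not drawn.

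The rule makes sense in SAD and MAD, where each dose cohort needs a set number of active and placebo ears and nothing is tested. Expansion is where ASP0598 is formally compared with placebo, and those tests rest on random assignment. Two further consequences follow. A replacement may fall in the other size stratum. And because a replaced subject can stay in the FAS, an arm that loses more subjects can end up with more members.

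**Working it through.** **1. The plan's own sample size.** Inputs from protocol 9.1: closure 10% and 80%, two-sided 0.05, power above 90%, drop-out 10%. Exact Fisher power is 84.1% at 10 per group and 90.5% at 11. Drop-out: 11 / 0.9 = 12.2, rounded up to 13. The stated 11 and 13 are reproduced.

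**2. How many replacements.** At the planned drop-out, 0.10 × 13 = 1.3 per arm, or 2.6 over two arms and 3.9 over three. These are figures for every drop-out being replaced; replacement is optional.

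**3. Chance of a stratum mismatch.** Let q be the share of subjects at or below 15%, which the documents do not give. If stratum is ignored, a replacement differs from the original with probability 2q(1 − q):
- q = 30% or 70%: 2 × 0.3 × 0.7 = 42%
- q = 50%: 2 × 0.5 × 0.5 = 50%

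With two replacements, the chance of at least one mismatch is 1 − 0.58² = 66% to 1 − 0.50² = 75%.

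**4. Shift in one arm's stratum share.**
- Original stays in the FAS, so the arm has 14. The largest possible shift is from 0/13 to 1/14 = 7.1 points. From a typical 6/13 = 46.2%, the share moves to 6/14 = 42.9% or 7/14 = 50.0%, a shift of 3.3 or 3.8 points.
- Original not in the FAS, so the arm has 13. One mismatch moves the share by 1/13 = 7.7 points.

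**5. Effect on the closure test, by simulation.** Assumptions not in the documents: 13 per arm, stratified blocks of 2, half the subjects in each stratum, replaced subjects left out of the analysis. The test is the plan's Mantel-Haenszel test with its Fisher fallback. Null closure rates for small and large perforations are 15%/5% or 70%/30% in both arms. For power they are 15%/5% on placebo and 85%/75% on active.

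| Replacements | Mean stratum difference (subjects) | Null rejection, 15%/5% | Null rejection, 70%/30% | Power |
|---|---|---|---|---|
| None | 0.5 | 0.41% | 1.80% | 97.1% |
| One per arm, same stratum | 0.5 | 0.39% | 1.95% | 96.8% |
| One per arm, any stratum | 0.9 | 0.53% | 1.71% | 97.5% |
| Two per arm, any stratum | 1.2 | 0.43% | 2.31% | 96.7% |
| Four, active arm only, all small perforations | 2.0 | 0.53% | 2.45% | 97.6% |

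**6. When the stratified adjustment is lost.** With arms equal within each stratum, the expected active-arm closures are half the total, so fewer than 10 closures overall fails the Mantel-Fleiss criterion. Assuming strata of 7 and 6 per arm and 10% placebo closure, the criterion fails in about 15% of trials at 80% active closure, 61% at 60% and 81% at 50%. The lower rates matter mainly for a low-dose comparison, for which the plan assumes no closure rate.

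**The case against.** The strongest reply is that the stratum point rests on silence. Protocol 6.3.6 makes no exception to stratification for replacements, keeps allocation central, and leaves procedure to an IRT manual that is not among the documents. Same-stratum replacement fits every sentence. That stands, and it is why balance *can be* disturbed and not *is*. It does not touch the main point: the inherited treatment is a stated rule, and matching would not turn it into a random draw.

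Second, the analysis largely absorbs a size imbalance. The Mantel-Haenszel test adjusts for size group, and the MMRMs carry the baseline size or ratio with its interaction by week. This also stands, except under the Fisher fallback. The simulation includes that fallback and shows no rejection rate near 5%.

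Third, optional replacement protects the group size if losses exceed 10% or subjects are randomised and never dosed. The latter are outside the FAS and SAF, so nothing is counted twice. That is a fair reason to want extra subjects, but it does not require the extra subject to inherit a treatment.

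A reader might infer that the sponsor could choose whom to replace knowing the arm. The documents do not support this. Protocol 6.3.5 describes sponsor code-breaking for SUSARs by limited personnel, 4.1.1.3 has the DEC request assignments from the study statistician, and IRT could assign the inherited treatment without disclosing it. What remains is that the text does not say that those who decide on replacement are blinded.

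**Conclusion.** The point holds as a minor weakness in allocation integrity. In expansion a replacement's treatment is inherited, at sponsor discretion and without a stated trigger, and so is not drawn under 6.3.6. Nothing in the documents requires a stratum match or says how the FAS treats the pair.

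The size is small. The mean between-arm stratum difference is about 0.9 subjects with one replacement per arm and 1.2 with two, against 0.5 with none. Null rejection stayed at or below 2.5% and power at about 97%. These figures depend on the assumed equal strata, blocks of 2 and number of replacements. The runs also leave replaced subjects out, whereas the FAS keeps those who were dosed and assessed, so they do not cover the case where both count.

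Two stronger readings are tempting. One is that the stratified balance is broken. It moves only when strata differ, and a one-for-one swap leaves arm totals unchanged. The other is that each mismatch shifts an arm by 7.7 points. That needs the original to be outside the FAS; where the original stays, the limit is 7.1 points and 3 to 4 is typical. No bias in the treatment comparison has been demonstrated. The affected closure test is a secondary endpoint in a study whose primary objective is safety.

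**What to change.** In protocol 4.1, the synopsis and SAP 2.3, limit inherited-treatment replacement to SAD and MAD. For dose expansion, choose one of these:
- Allocate any additional subject through IRT on the next unused number in that subject's own TMP size stratum.
- Do not replace. Thirteen per group already allows for 10% drop-out, and the closure estimand (protocol 3.2.3) carries forward the status just before discontinuation.

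In either case, state in protocol 9.2.1 and SAP 4.1 that a subject who was dosed and otherwise meets the FAS definition stays in it whether or not another subject is added. If inherited replacement is kept in expansion, state the triggers, require the same stratum and blinded decision-makers, and say how both subjects enter the FAS.

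The cost is a few sentences in two documents and an IRT setting. Arms may end one or two subjects unequal, which costs little: exact Fisher power at 10% versus 80% is 97.0% with 13 per arm, and 96.9% with 12 on placebo and 14 on active.
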